5.2.3 Day 15 of all Cycles

- Serum chemistries: Phosphorus, Magnesium, LDH and Comprehensive metabolic panel (CMP) to include: albumin, alkaline phosphatase, ALT/SGPT, AST/SGOT, BUN, creatinine, electrolytes (sodium, potassium, calcium, chloride, bicarbonate), glucose, and total bilirubin.
- Hematology

5.2.4 One day of week 3 of Cycle 2 only

- Octreotide scan

5.2.5 One Day of Week 3 of every other Cycle (starting with Cycle 2)

- Serum Chromogranin
- Tumor Assessment

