4.2.1.1 Dose Levels and Reductions

Study medication will be administered on a 3 weeks on/1week off schedule [3 weeks out of every 4]. A new cycle of therapy can start when all toxicities, (except hand-foot syndrome, alopecia, non-refractory nausea/vomiting, non-refractory hypersensitivity and nonclinical and asymptomatic laboratory abnormalities) have resolved to Grade 2 or less. Hand-foot syndrome must have resolved to Grade 0-1.

Doses will be delayed or reduced for clinically significant hematologic and non-hematologic toxicities that are related to protocol therapy according to the guidelines shown in the Dose Delays/Dose Modifications table that follows. Dose modifications will follow predefined dose levels. Dose adjustments for hematologic toxicity are based on the blood counts obtained in preparation for the day of treatment.

Strictly follow the modification in the following tables for the first **two** cycles until individual treatment tolerance can be ascertained. Thereafter, these modifications should be regarded as guidelines to produce mild-to-moderate, but not debilitating, side effects. If multiple adverse events are seen, administer dose based on greatest reduction required for any single adverse event observed. Reductions or increases apply to treatment given in the preceding cycle and are based on adverse events observed since the prior dose.

Dose Level			If no SDRT	If + SDRT**
Dose level 0*	80 mg po qd	Two 40-mg tablets of regorafenib	Proceed to next dose level	
Dose level 1	120 mg po qd	Three 40-mg tablets of regorafenib	Proceed to next dose level	Decrease to 80 mg
Dose level 2	160 mg po qd	Four 40-mg tablets of regorafenib		Decrease to 120 mg
* Starting Dose				
** SDRT= Significant Drug Related Toxicities				

If a subject experience more than one toxicity, dose reduction should be according to the toxicity with the highest grade

In the case of two or more toxicities of the same grade, the investigator may dose reduce according to that deemed most causally related to study treatment

The following tables outline dose adjustments for toxicities related to study drug except hand-foot skin reaction, hypertension and liver function test abnormalities.

NCI-CTCAE v4.0 ^a	Dose Interruption	Dose Modification ^b	Dose for Subsequent Cycles
Grade 0-2	Treat on time	No change	No change

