Grade 3	Delay until \leq Grade 2 ^c	Reduce by 1 dose level	If toxicity remains < Grade 2, dose re-escalation can be considered at the discretion of the treating investigator. If dose is re-escalated and toxicity (\geq Grade 3) recurs, institute permanent dose reduction.
Grade 4	Delay until \leq Grade 2 ^c	Reduce by 1 dose level. Permanent discontinuation can be considered at treating investigator's discretion.	

- a. NCI-CTCAE = National Cancer Institute - Common Terminology Criteria for Adverse Events, version 4.0
- b. Excludes alopecia, non-refractory nausea/vomiting, lymphocyte count decreased, non-refractory hypersensitivity and nonclinical and asymptomatic laboratory abnormalities.
- c. If no recovery after a 4 week delay, treatment should be permanently discontinued unless subject is deriving clinical benefit.

The table above outlines dose adjustments for hematologic and non-hematologic toxicities related to regorafenib except HFSR and hypertension.

In addition to these recommended dose modifications, subjects who develop diarrhea, mucositis, anorexia or other events predisposing to fluid loss or inadequate fluid intake should be carefully monitored and rehydrated as clinically necessary. This is in order to minimize the risk of postural hypotension and renal failure.

	Grade 1	Grade 2	Grade 3
NCI-CTCAE v4.0 Palmar-plantar erythrodysesthesia syndrome ^a	Minimal skin changes or dermatitis (e.g., erythema, edema, or hyperkeratosis) without pain	Skin changes (e.g., peeling, blisters, bleeding, edema, or hyperkeratosis) with pain	Severe skin changes (e.g., peeling, blisters, bleeding, edema, or hyperkeratosis) with pain
Further description / examples of skin changes	Numbness, dysesthesia/paresthesia tingling, painless swelling, or erythema of the hands and/or feet	Painful erythema and swelling of the hands and/or feet	Moist desquamation, ulceration, blistering, or severe pain of the hands and/or feet
Effect on activities	Does not disrupt normal activities	Limiting instrumental activities of daily life (e.g., preparing meals, shopping for groceries or clothes, using the telephone, managing money)	Limiting self-care activities of daily life (e.g., bathing, dressing and undressing, feeding self, using the toilet, taking medications) and not bedridden
a. Palmer-planter erythrodysesthesia syndrome is a disorder characterized by redness, marked discomfort, swelling, and tingling in the palms of hands or the soles of the feet.			

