5.4 Study Calendar

Cycles will be 28 Days. Regorafenib will be taken orally Days 1-21 of each Cycle. For first cycle all labs and EKG should be done within 7 days of first receiving study drug. For the first cycle, Imaging studies should be done within 28 days of first receiving study drug.

Parameter	Pre-Treatment ⁶	Day 1 of All Cycles ¹ ²	Day 8, Day 15 And 22 of Cycle 1 and 2 only ¹²	Day 15 of all Cycles ¹ ²	One Day of Week 3 Of every other Cycle (starting with Cycle 2)	Off study	Follow-up
Informed Consent	X						
Pill Diary		X				X	
History & Physical Exam	X	X					
Weight, SWOG Performance Status, Con Meds	X	X				X	
Adverse Event/Toxicity Evaluation	X	X					
WBC (differential), Hgb, Platelets	X	X		X			
Complete Metabolic Panel, Phosphorus, Magnesium, LDH	X	X	Liver function	X			
Lipase	X	X					
Thyroid Function (TSH, T3, T4)	X	X ³					
PT/PT-INR, PTT	X	X ^{3,9}					
Urinalysis for proteinuria	X	X					
5HIAA	X	X					
Serum Chromogranin	X				X		
Octreotide scan	X				Cycle 2 only		
EKG	X	X ³					
CXR (if CT of chest not done)	X ⁷				X ⁷		
BP Monitoring		X	X				
Radiology, x-ray or Scans for disease measurement ²	X ⁸				X		X ¹⁰
Archival tumor tissue	X ⁸						
Plasma	X ⁸					X ⁸	
Urine Pregnancy Test	X ⁵	X ⁵					
Survival Follow-up							X ¹¹

- 1 If used to follow measurable disease.
- 2 Within 28 days of Cycle 1, Day 1.
- 3 As clinically indicated.
- 4 Paraffin embedded tissue must be available for review.
- 5 For women of childbearing potential
- 6 Confirm response within 4 weeks.
- 7 Not required if CT scan of the chest is done.
- 8 See section 9. For plasma two purple top tubes to the [name] lab.
- 9 Close monitoring (day 5 of cycle 1 and day 1 of each cycle) of PT/PT-INR and PTT is mandatory for patients on agents such as warfarin and heparin.
- 10 Patients that come off for reasons other than disease progression will have their standard of care scans measured via RECIST until progressive disease, to determine date of disease progression
- 11 Patients will be followed up via phone call, medical records or database search until death to determine survival time
- 12 All study visits allow a +/- 7 day window

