6.1.9 Overall Survival (OS)

Overall survival is defined as from start of treatment until death due to any cause. Otherwise OS is censored on the last day patients are known to be alive.

6.1.10 The primary endpoint:

The 6-month PFS rate is the primary endpoint. The 6-month PFS is dichotomous, *yes* or *no*. Radiographic scan for disease measurement that is done within ± 14 days of the 6-month landmark (Day 182 since first receiving study drug) will be counted to determine the 6-month PFS status. Patients who are alive and progression-free at 6 months (182 days) since first starting regorafenib will be counted as 'yes' for the 6-month PFS. Patients who progress or die within 6 months of starting regorafenib will be counted as 'no' for the 6-month PFS. Patients whose status of progression or death at 6 months is unknown due to early withdrawal, loss-of-follow-up, or other reasons will be also counted as 'no' for 6-month PFS.

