10.3 Data Analyses Plans

Two cohorts will be analyzed separately. The primary data analysis set will include all patients who enroll the study and start to receive regorafenib for decision making in accrual and warranting further studies. Patients who withdraw the study, are lost to follow-up, or start another therapy before the status of 6-month PFS is determined will be counted as 'no' for the primary endpoint and be included in the primary data analysis set. Patients who drop out the trial before starting regorafenib will be replaced and excluded from the primary data analysis set.

The primary endpoint, 6-month PFS rate will be summarized as a proportion of patients who are alive and progression-free among all patients in the primary data analysis set. The 95% confidence intervals of the 6-month PFS rate will be calculated using the Wilson method. We chose 6-month as the cut-off point because it would be easier to compare with the historical data. The tumor response will be evaluated by CT scans every 2 cycles starting with week 3 of cycle 2. Six-months since starting treatment are 182 days, may not be on the CT scan date. CT scans will not on the strict schedules. Additional scans may be conducted to confirm a complete or partial response. Patients whose systems deteriorate clinically will be counted as progression event without confirmation of CT scans. CT scans that are conducted within ± 14 days of the landmark Day 182 will be used to determine the 6-month PFS status if there are no other scans available to determine the status. The detailed status of 6-month PFS will be counted as follows: alive and progression-free, disease progression within 6 months, death within 6 months, and progression at 6 months unknown due to early withdrawal, toxicities, or other reasons.

A sensitivity analysis of PFS at week 24 will be conducted. The PFS rate at week 24 may provide the impact of CT scheduling on estimating the 6-month PFS rate.

In addition, progression-free survival (see definition at section 6.1.7) will be analyzed using Kaplan-Meier curves. The median PFS and 95% CIs will be calculated. The probability of 6-month PFS will be estimated from the KM curve too.

The secondary endpoints including tumor response rate and OS (see definition at section 6.1.9) will be analyzed descriptively.

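### Tumour scans follow the cycle count while 6-month PFS runs from first dose, so toxicity delays decide when progression is looked for

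*Combined protocol and SAP*

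**What the plan says.** **Scans are counted in cycles.** Section 5.2.5 sets tumour assessment on "One Day of Week 3 of every other Cycle (starting with Cycle 2"), and the Section 5.4 calendar has the same column. Section 10.3 repeats it: "The tumor response will be evaluated by CT scans every 2 cycles starting with week 3 of cycle 2". Section 5.4 gives the nominal length, "Cycles will be 28 Days", and adds "All study visits allow a +/- 7 day window".

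**Cycles can be postponed.** Section 4.2.1.1 makes the start of a cycle conditional: "A new cycle of therapy can start when all toxicities" (with listed exceptions) have come down to Grade 2 or less, and hand-foot syndrome to Grade 0-1. Footnote c of the general toxicity table reads: "If no recovery after a 4 week delay, treatment should be permanently discontinued unless subject is deriving clinical benefit".

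**The endpoint runs on calendar time.** Section 6.1.10: "Patients who are alive and progression-free at 6 months (182 days) since first starting regorafenib will be counted as 'yes' for the 6-month PFS". Section 10.3: "CT scans that are conducted within ± 14 days of the landmark Day 182 will be used to determine the 6-month PFS status". Unknown status is scored 'no'. PFS in Section 6.1.7 also starts at first treatment.

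No section keeps on-treatment scans on schedule when a cycle slips.

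**The concern.** There are two clocks. A cycle delay moves every later scan, but Day 182 does not move. Two patients with the same tumour course can then be scored differently because one tolerated the drug better. The trial is single-arm, so no control group shares the effect. Each cohort has 24 patients and a fixed cut-off (14 in A, 18 in B), so a few rescored patients can change the decision. The planned Kaplan-Meier analysis uses the same displaced scans.

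**Working it through.** **1. The plan's own figures.** Exact two-stage binomial, from the rules in Section 10.2: P(promising) = sum over x ≥ c of b(x; 11, p) × P(Bin(13, p) ≥ r − x).
- Cohort A (c = 5, r = 14): type I error 0.0514 at p = 0.40, power 0.8049 at p = 0.65.
- Cohort B (c = 7, r = 18): type I error 0.0531 at p = 0.57, power 0.8015 at p = 0.80.

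These match the stated 5.1%, 5.3% and 80%. They hold if the scored rate equals the true 6-month rate.

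**2. Scan days.** With first dose on Day 1, week 3 of cycle k covers Days 28(k−1)+15 to 28(k−1)+21, plus accumulated delay. The counting window is 182 ± 14, that is Days 168 to 196.

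| Accumulated delay (days) | Cycle 4 | Cycle 6 | Cycle 8 | Nominal week-3 scan in window? |
|---|---|---|---|---|
| 0 | 99-105 | 155-161 | 211-217 | none |
| 7 | 106-112 | 162-168 | 218-224 | cycle 6, last day only |
| 14 | 113-119 | 169-175 | 225-231 | cycle 6 |
| 21 | 120-126 | 176-182 | 232-238 | cycle 6 |
| 35 | 134-140 | 190-196 | 246-252 | cycle 6 |
| 42 | 141-147 | 197-203 | 253-259 | none |
| 56 | 155-161 | 211-217 | 267-273 | none |

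Delays of 7 to 41 days bring the cycle 6 scan into the window (161 + 7 = 168; 155 + 41 = 196). With no delay, the 7-day visit allowance reaches Day 168 at the latest (161 + 7).

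**3. Same tumour, two scores.** Take mid-week-3 scans (cycle day 18, so cycle 6 nominally on Day 158) and progression visible from Day 175.
- 14-day delay: scan on Day 172, clean, in the window: 'yes'.
- 21-day delay: scan on Day 179, progression, in the window: 'no'.

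This needs no survival model and no disputed reading of the scoring rule.

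**4. Size for one patient (illustration).** Assumptions not in the documents: exponential PFS, null true, mid-week-3 scans. Then S(t) = p0^(t/182), where t is the day of the scan that decides. First, score 'yes' unless progression is documented:

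| Case | Deciding scan | P(yes), A (target 0.40) | P(yes), B (target 0.57) |
|---|---|---|---|
| No delay | Day 158 | 0.45 | 0.61 |
| Delay 10-38 days | Cycle 6, Days 168-196 | 0.43-0.37 | 0.59-0.55 |
| Cycle 6 scan after Day 196 | Cycle 4, Days 144-102 | 0.48-0.60 | 0.64-0.73 |

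Second, treat a patient with no scan in the window and progression at the next scan as unknown, hence 'no'. With no delay the deciding scan is Day 214: S = 0.34 (A) and 0.52 (B). With a 42-day delay it is Day 200: 0.365 and 0.539. All are below target.

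**5. Size for a cohort (illustration).** Put the same delay on every patient and enter S(t) in the formula of step 1:

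| Delay (days) | Type I error, A | Type I error, B |
|---|---|---|
| 0 | 13.2%, or 1.2% if unknown = 'no' | 11.8%, or 1.6% |
| 14 | 7.7% | 7.5% |
| 35 | 3.2% (power 75%) | 3.6% (power 76%) |
| 42 | 21.5%, or 2.3% if unknown = 'no' | 18.0%, or 2.8% |

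The departure at zero delay comes from where the nominal scans sit, which is a separate matter. The part that belongs to this point is the change with delay.

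**The case against.** **A reader might infer that toxicity delays favour regorafenib.** If 20% of patients have their last usable scan on Days 102-123 and the rest are undelayed, scoring 'yes' unless progression is documented raises the false-positive rate from 13% to 17-21% (A) and from 12% to 15-17% (B). The arithmetic reproduces, but the documents do not support the inference. They give no delay frequency; at 10% instead of 20% the result is 15-17% and 13-14%. The calculation also leaves out short delays, which act the other way: with an assumed 40% of patients spread over Days 168-196, it returns to 13-15% (A) and 11-13% (B), close to the undelayed values. If unknown is scored 'no', the direction reverses, and Section 10.3 lists toxicities among the reasons for unknown status.

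**Long delays are restricted.** Passing Day 196 needs at least 39 days of accumulated delay (158 + 39 = 197). For hand-foot skin reaction and hypertension, the tables end treatment after more than 4 weeks of delay. The documents also do not say that an interruption within a cycle lengthens it. This limits the long-delay group but leaves the shorter delays of step 3 untouched.

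**Moderately delayed patients are the better timed ones.** This is correct: their P(yes) brackets the target. It is an argument about which calendar days to choose, not for letting toxicity choose them.

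**The plan already allows for loose timing.** Section 10.3 concedes that Day 182 may not be a scan date, counts clinical deterioration as progression, and adds a week-24 analysis and a Kaplan-Meier estimate. Footnote 10 of Section 5.4 continues RECIST reading after treatment stops. These soften the problem. None moves an on-treatment scan back, and the week-24 analysis (Day 168) relies on the same scans.

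**The 28-day cycle might be read as a fixed calendar.** Section 4.2.1.1 makes the start of a cycle conditional on recovery, so that reading fails.

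**Conclusion.** The point holds as a design weakness. When progression is looked for depends on tolerability, and the same tumour course can score 'yes' or 'no'. The scan-day arithmetic rests on the documents alone, apart from taking cycle day 18 in the example.

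Neither the direction nor the net size of the bias can be determined. Both depend on the frequency and length of delays and on how a patient without a decisive scan is scored, and the documents settle neither. The ranges for one patient (0.37 to 0.60 in A, 0.55 to 0.73 in B) show how far delay can move the score under exponential PFS and 'yes' unless progression is documented. They are not estimates of the cohort's bias.

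For Kaplan-Meier PFS, a 4-week delay after the cycle 4 scan widens that gap from 56 to 84 days. Taking the mean detection lag as half the gap, it grows by (84 − 56)/2 = 14 days, but only for progressions inside that gap.

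The change is worth making because it is cheap and touches the primary endpoint.

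**What to change.** In Sections 5.2.5, 5.4 and 10.3, schedule tumour assessments by time since first dose, irrespective of dose holds or cycle delays, at about 8-week intervals with a window of 7 days either side. Choose the days so that one planned scan falls inside Days 168 to 196, for example close to Day 182. A planned day from 175 to 189 keeps the whole visit window inside (168 + 7; 196 − 7).

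Do not freeze the present nominal Days 46, 102, 158 and 214. That would remove the dependence on tolerability but put every patient's scan outside the window, with a false-positive rate of about 13% (A) and 12% (B) if 'yes' is scored unless progression is documented.

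**Cost.** Wording in three places. A delayed patient's scan may not coincide with a cycle visit, and such patients have slightly more scans per cycle. On a strict 56-day grid through Day 182, the scans fall on Days 70, 126 and 182: still three by the landmark, but the first is 24 days later than the present Day 46. The sponsor can accept that, or use slightly uneven intervals or one extra early scan.

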5.2.6 Off Study

- Pill Diary
- SWOG Performance Status
- Vital Signs
- Blood draw for correlative studies - Two purple top tubes to the [name] lab, See Section 9.0 for details

5.3 Follow-up Procedures

Patients will be followed with phone calls every 3 months until death after removal from treatment. Patients removed from treatment for unacceptable adverse events will be followed until resolution or stabilization of the adverse event.

5.4 Study Calendar

Cycles will be 28 Days. Regorafenib will be taken orally Days 1-21 of each Cycle. For first cycle all labs and EKG should be done within 7 days of first receiving study drug. For the first cycle, Imaging studies should be done within 28 days of first receiving study drug.

Parameter	Pre-Treatment ⁶	Day 1 of All Cycles ¹ ²	Day 8, Day 15 And 22 of Cycle 1 and 2 only ¹²	Day 15 of all Cycles ¹ ²	One Day of Week 3 Of every other Cycle (starting with Cycle 2)	Off study	Follow-up
Informed Consent	X						
Pill Diary		X				X	
History & Physical Exam	X	X					
Weight, SWOG Performance Status, Con Meds	X	X				X	
Adverse Event/Toxicity Evaluation	X	X					
WBC (differential), Hgb, Platelets	X	X		X			
Complete Metabolic Panel, Phosphorus, Magnesium, LDH	X	X	Liver function	X			
Lipase	X	X					
Thyroid Function (TSH, T3, T4)	X	X ³					
PT/PT-INR, PTT	X	X ^{3,9}					
Urinalysis for proteinuria	X	X					
5HIAA	X	X					
Serum Chromogranin	X				X		
Octreotide scan	X				Cycle 2 only		
EKG	X	X ³					
CXR (if CT of chest not done)	X ⁷				X ⁷		
BP Monitoring		X	X				
Radiology, x-ray or Scans for disease measurement ²	X ⁸				X		X ¹⁰
Archival tumor tissue	X ⁸						
Plasma	X ⁸					X ⁸	
Urine Pregnancy Test	X ⁵	X ⁵					
Survival Follow-up							X ¹¹

- 1 If used to follow measurable disease.
- 2 Within 28 days of Cycle 1, Day 1.
- 3 As clinically indicated.
- 4 Paraffin embedded tissue must be available for review.
- 5 For women of childbearing potential
- 6 Confirm response within 4 weeks.
- 7 Not required if CT scan of the chest is done.
- 8 See section 9. For plasma two purple top tubes to the [name] lab.
- 9 Close monitoring (day 5 of cycle 1 and day 1 of each cycle) of PT/PT-INR and PTT is mandatory for patients on agents such as warfarin and heparin.
- 10 Patients that come off for reasons other than disease progression will have their standard of care scans measured via RECIST until progressive disease, to determine date of disease progression
- 11 Patients will be followed up via phone call, medical records or database search until death to determine survival time
- 12 All study visits allow a +/- 7 day window

6.0 Measurement of Effect

6.1 Antitumor Effect- Solid Tumors

Response and progression will be evaluated in this study using the new international criteria proposed by the Response Evaluation Criteria in Solid Tumors (RECIST) Committee [*JNCI* 92(3):205-216, 2000]. Changes in only the largest diameter (unidimensional measurement) of the tumor lesions are used in the RECIST v1.1 criteria.

6.1.1 Definitions

Evaluable for toxicity. All patients will be included in the toxicity summaries, from the time of their first treatment with study drug.

All patients must be accounted for in the summary of objective response (see Section 10.4 for more details). To formally classify a patient as RECIST-evaluable, only those patients who have measurable disease present at baseline, and have had their disease re-evaluated will be considered evaluable. These patients will have their response classified according to the definitions stated below. (Note: Patients who exhibit objective disease progression prior to the end of Cycle 1 will also be considered evaluable.)

6.1.2 Disease Parameters (RECIST 1.1)

Measurable disease. Measurable lesions are defined as those that can be accurately measured in at least one dimension (longest diameter to be recorded) as ≥ 20 mm with conventional techniques (CT, MRI, x-ray) or as ≥ 10 mm with spiral CT scan. All tumor measurements must be recorded in millimeters (or decimal fractions of centimeters).

Note: Previously irradiated lesions are non-measurable except in cases of documented progression of the lesion since the completion of radiation therapy.

Non-measurable disease. All other lesions (or sites of disease), including small lesions (longest diameter < 20 mm with conventional techniques or < 10 mm using spiral CT scan), are considered non-measurable disease. Bone lesions, leptomeningeal disease, ascites, pleural/pericardial effusions, lymphangitis cutis/pulmonis, inflammatory breast disease, abdominal masses (not followed by CT or MRI), and cystic lesions are all non-measurable.

Target lesions. All measurable lesions up to a maximum of 2 lesions per organ and 5 lesions in total, representative of all involved organs, should be identified as **target lesions** and recorded and measured at baseline. Target lesions should be selected on the basis of their size (lesions with the longest diameter) and their suitability for accurate repeated measurements (either by imaging techniques or clinically). A sum of the longest diameter (LD) for all

target lesions will be calculated and reported as the baseline sum LD. The baseline sum LD will be used as reference by which to characterize the objective tumor response.

Malignant lymph nodes. To be considered pathologically enlarged and measurable, a lymph node must be >15 mm in short axis when assessed by CT scan (CT scan slice thickness recommended to be no greater than 5 mm). At baseline and in follow-up, only the short axis will be measured and followed.

Non-target lesions. All other lesions (or sites of disease) including any measurable lesions over and above the 5 target lesions should be identified as **non-target lesions** and should also be recorded at baseline. Measurements of these lesions are not required, but the presence or absence of each should be noted throughout follow-up.

6.1.3 **Methods for Evaluation of Measurable Disease**

All measurements should be taken and recorded in metric notation using a ruler or calipers. All baseline evaluations should be performed as closely as possible to the beginning of treatment and never more than 28 days before the beginning of the treatment.

The same method of assessment and the same technique should be used to characterize each identified and reported lesion at baseline and during follow-up. Imaging-based evaluation is preferred to evaluation by clinical examination when both methods have been used to assess the antitumor effect of a treatment.

Conventional CT and MRI. These techniques should be performed with cuts of 10 mm or less in slice thickness contiguously. Spiral CT should be performed using a 5 mm contiguous reconstruction algorithm. This applies to tumors of the chest, abdomen, and pelvis.

Cytology, Histology. These techniques can be used to differentiate between partial responses (PR) and complete responses (CR) in rare cases (e.g., residual lesions in tumor types, such as germ cell tumors, where known residual benign tumors can remain).

The cytological confirmation of the neoplastic origin of any effusion that appears or worsens during treatment when the measurable tumor has met criteria for response or stable disease is mandatory to differentiate between response or stable disease (an effusion may be a side effect of the treatment) and progressive disease.

6.1.4 **Response Criteria**

6.1.4.1 **Evaluation of Target Lesions**

Complete Response (CR): Disappearance of all target lesions, determined by two separate observations conducted not less than 4 weeks apart.

There can be no appearance of new lesions.

Partial Response (PR): At least a 30% decrease in the sum of the longest diameter (LD) of target lesions, taking as reference the baseline sum LD. There can be no appearance of new lesions.

Progressive Disease (PD): At least a 20% increase in the sum of the LD of target lesions, taking as reference the smallest sum LD recorded since the treatment started, or the appearance of one or more new lesions.

Stable Disease (SD): Neither sufficient shrinkage to qualify for PR nor sufficient increase to qualify for PD, taking as reference the smallest sum LD since the treatment started.

